5.1.3 Definition of Dose Limiting Toxicity

All toxicities will be graded using NCI CTCAE Version 4.0 based on the investigator assessment. The DLT window of observation will be during first **21-days** of treatment for Cohort A and first **28-days** of treatment for Cohorts B, C, D, and E to align with chemotherapy regimen.

The occurrence of any of the following toxicities will be considered a DLT, if assessed by the investigator to be possibly, probably or definitely related to study drug administration, excluding toxicities clearly not related to the drug, such as disease progression, environmental factors, unrelated trauma, etc.:

1. Grade 4 non-hematologic toxicity (not laboratory).
2. Grade 4 hematologic toxicity lasting >7 days.
3. Grade 3 thrombocytopenia associated with clinically significant bleeding.
4. Any non-hematologic AE Grade ≥ 3 in severity despite optimal supportive care should be considered a DLT, with the following exceptions:
 - Grade 3 fatigue lasting ≤ 3 days;
 - Grade 3 diarrhea, nausea, or vomiting without use of anti-emetics or anti-diarrheals per SOC;
 - Grade 3 rash without use of corticosteroids or anti-inflammatory agents per SOC.
5. Any Grade 3 or Grade 4 non-hematologic laboratory value if:
 - Medical intervention is required to treat the participant, or
 - The abnormality leads to hospitalization, or
 - The abnormality persists for >1 week.
6. Febrile neutropenia Grade 3 or Grade 4:
 - Grade 3 is defined as ANC $<1000/\text{mm}^3$ with a single temperature of $>38.3^\circ\text{C}$ (101°F) or a sustained temperature of $\geq 38^\circ\text{C}$ (100.4°F) for more than 1 hour.

- Grade 4 is defined as ANC <1000/mm³ with a single temperature of >38.3 degrees C (101 degrees F) or a sustained temperature of ≥38 degrees C (100.4 degrees F) for more than 1 hour, with life-threatening consequences and urgent intervention indicated.

7. Any prolonged delay (>2 weeks) in initiating study therapy due to a treatment-related AE that started during the DLT period:

8. Any treatment-related toxicity that causes the participant to discontinue treatment during the DLT period.

9. Missing >25% of binimetinib doses as a result of drug-related AE(s) during the DLT period.

10. Grade 5 toxicity

11. Cardiac disorders

- Absolute decrease in LVEF >10% compared with baseline and the LVEF is below the institution's lower limit of normal
- Left ventricular systolic dysfunction Grade ≥3
- Other cardiac disorders Grade ≥3

12. Vascular disorders

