6.1 Inclusion Criteria

Participants are eligible to be included in the study only if all of the following criteria apply:

1. Male and female participants who are at least 18 years of age on the day of signing consent will be eligible for enrollment in the study.
2. Have a histologically-confirmed, unresectable or metastatic (Stage IV American Joint Committee on Cancer seventh edition) CRC.
3. Have a locally determined non-MSI-H/pMMR tumor status (Section 5.4.1.6).
4. Have at least 1 radiologically measurable lesion as defined by RECIST 1.1.
5. Have an ECOG performance status of 0 or 1 prior to treatment initiation.
6. Have a life expectancy of at least 3 months.

7. Participants must have the ability to swallow and retain oral medication and not have any clinically significant gastrointestinal abnormalities that might alter absorption.
8. Have adequate organ function as defined in **Table 4**. All screening labs should be performed within 10 days prior to the first dose of trial treatment.

Table 4 Inclusion Criteria Laboratory Parameters

Hematological	
Absolute neutrophil count (ANC)	$\geq 1,500/\text{mcL}$
Platelets	$\geq 100,000/\text{mcL}$
Hemoglobin	$\geq 9.0 \text{ g/dL}$ or $\geq 5.6 \text{ mmol/L}$
Renal	
Serum creatinine OR Calculated* serum creatinine clearance (GFR can be used in place of creatinine or creatinine clearance)	$\leq 1.5 \times$ upper limit of normal (ULN) OR $\geq 60 \text{ mL/min}$ for participants with creatinine levels $>1.5 \times$ institutional ULN
Hepatic	
Serum total bilirubin	$\leq 1.5 \times$ ULN or direct bilirubin \leq ULN for participants with total bilirubin >1.5 ULN
AST (SGOT) and ALT (SGPT)	$\leq 2.5 \times$ ULN OR $\leq 5.0 \times$ ULN for participants with liver metastases
Albumin	$\geq 3.0 \text{ g/L}$
Coagulation	
International Normalized Ratio (INR) or prothrombin time (PT) or activated partial thromboplastin time (aPTT)	$\leq 1.5 \times$ ULN unless participant is receiving anticoagulant therapy as long as the PT or aPTT is within the therapeutic range for the intended use of the anticoagulants

*Calculate serum creatinine clearance using the standard Cockcroft-Gault formula.
Abbreviations: ALT=alanine aminotransferase; AST=aspartate aminotransferase; GFR= glomerular filtration rate; INR=International Normalized Ratio; SGOT=serum glutamic oxaloacetic transaminase; SGPT= serum glutamic-pyruvic transaminase; ULN = upper limit of normal.

Participants for Cohort A

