Grade 3	Interrupt binimatinib and refer the participant to ophthalmologist within 1 week and obtain OCT: 
 • If resolved to baseline or Grade ≤ 2 within 7 days, resume treatment at current dose level and continue schedule of visual assessments established per protocol. • If not resolved to baseline or Grade ≤ 2 within 7 days, continue to hold the binimatinib dose and repeat ophthalmic assessment in 10 days. 
 ◦ If resolved to baseline or Grade ≤ 2, resume treatment at reduced dose level and continue schedule of visual assessments established per protocol. ◦ If remains Grade 3, permanently discontinue binimatinib.
Grade 4	Permanently discontinue binimatinib and immediately follow up with ophthalmic monitoring.
Eye disorder - RVO	
Any Grade	Permanently discontinue binimatinib.
Other eye disorders (i.e. Non-retinal Events)	
Grade 1-2	Maintain dose level of binimatinib and increase frequency of ophthalmic monitoring to at least 14 days until stabilization or resolution.
Grade 3	Interrupt binimatinib and refer participant to ophthalmologist within 1 week: 
 • If resolved to Grade ≤ 1 in ≤ 21 days, reduce 1 dose level of binimatinib. • If not resolved to Grade ≤ 1 in ≤ 21 days, permanently discontinue binimatinib.
Grade 4	Permanently discontinue binimatinib.

Toxicity	Dose Adjustment for Binimetinib
Liver-related adverse events	
Grade 1 AST or ALT ($>$ ULN - 3 x ULN)	Maintain dose level of binimetinib.
Grade 2 AST or ALT ($>$ 3 - 5.0 x ULN or 3 x baseline value) AND blood bilirubin \leq 2.0 x ULN	
Interrupt dose of binimetinib until resolved to Grade \leq 1 (or Grade \leq 2 in case of liver metastasis), then:
 
 • If resolved in \leq 14 days, maintain dose level of binimetinib. • If resolved in $>$ 14 days, reduce dose level of binimetinib. 
Recurrence:
 
 • Interrupt dosing of binimetinib until resolved to Grade \leq 1 (or Grade \leq 2 in case of liver metastasis), then resume treatment at a reduced dose.

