Grade 2 AST or ALT ($>$ 3 - 5.0 x ULN or 3 x baseline value) AND blood bilirubin $>$ 2.0 x ULN	
Interrupt dose of binimetinib until resolved to Grade \leq 1 (or Grade \leq 2 in case of liver metastasis), then:
 
 • If resolved in \leq 7 days, resume treatment at a reduced dose of binimetinib. • If not resolved in \leq 7 days, permanently discontinue binimetinib.
Grade 3 AST or ALT ($>$ 5.0 - 8.0 x ULN) AND blood bilirubin \leq 2.0 x ULN	
Interrupt dose of binimetinib until resolved to Grade \leq 1 (or Grade \leq 2 in case of liver metastasis), then:
 
 • If resolved in \leq 14 days, maintain dose level of binimetinib. • If resolved in $>$ 14 days, reduce dose level of binimetinib. 
Recurrence:
 
 • Interrupt dosing of binimetinib until resolved to Grade \leq 1 (or Grade \leq 2 in case of liver metastasis), then resume treatment at a reduced dose.
AST or ALT ($>$ 8 x ULN) AND blood bilirubin* \leq 2.0 x ULN	Permanently discontinue binimetinib.
AST or ALT ($>$ 5.0 x ULN) AND blood bilirubin* $>$ 2.0 x ULN	Permanently discontinue binimetinib.
AST or ALT Grade 4 ($>$ 20.0 x ULN)	Permanently discontinue binimetinib.

Toxicity	Dose Adjustment for Binimetinib
Cardiac disorders	
Left ventricular systolic dysfunction Asymptomatic decrease of >10% in LVEF compared to baseline and the LVEF is below the institution's lower limit of normal	
Interrupt dose of binimetinib and repeat evaluation of LVEF within 2 weeks.
 
 • If the LVEF recovers (defined as LVEF \geq 50% or \geq LLN and absolute decrease \leq 10% compared to baseline) \leq 3 weeks, reduce 1 dose level after approval of the Sponsor Medical Monitor. Monitor LVEF 2 weeks after restarting on binimetinib, every 4 weeks for 12 weeks and subsequently as per protocol. • If the LVEF does not recover within 3 weeks, permanently discontinue participant from study treatment. Closely monitor LVEF until resolution (or 16 weeks).
Grade 3-4	Permanently discontinue participant from binimetinib. Closely monitor LVEF until resolution (or 16 weeks).
CK elevation	
Grade 1-2	
Continue treatment on same dose level. Ensure patient is adequately hydrated. Monitor closely CK and serum creatinine levels.
 
(If total CK \geq 3 X ULN, measure isoenzymes and myoglobin in blood and urine).

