9.3.7 Events of Clinical Interest (ECI)

Selected non-serious and serious adverse events are also known as Events of Clinical Interest (ECI) and must be reported to the Sponsor.

Events of clinical interest for this trial include:

1. an overdose of Sponsor's product, as defined in Section 9.4 – Treatment of Overdose, that is not associated with clinical symptoms or abnormal laboratory results.
2. an elevated AST or ALT lab value that is greater than or equal to 3X the upper limit of normal and an elevated total bilirubin lab value that is greater than or equal to 2X the upper limit of normal and, at the same time, an alkaline phosphatase lab value that is less than 2X the upper limit of normal, as determined by way of protocol-specified laboratory testing or unscheduled laboratory testing.*

*Note: These criteria are based upon available regulatory guidance documents. The purpose of the criteria is to specify a threshold of abnormal hepatic tests that may require an additional evaluation for an underlying etiology. The trial site guidance for assessment and follow up of these criteria can be found in the Investigator Trial File Binder (or equivalent).

For the time period beginning when the consent form is signed until treatment allocation/randomization, any ECI, or follow up to an ECI, that occurs to any participant must be reported within 24 hours to the Sponsor if it causes the participant to be excluded from the trial, or is the result of a protocol-specified intervention, including but not limited to washout or discontinuation of usual therapy, diet, placebo treatment or a procedure.

For the time period beginning at treatment allocation/randomization through 30 days following cessation of treatment, any ECI, or follow up to an ECI, whether or not related to the Sponsor's product, must be reported within 24 hours to the Sponsor, either by electronic media or paper. Electronic reporting procedures can be found in the EDC data entry

guidelines. Paper reporting procedures can be found in the Investigator Trial File Binder (or equivalent).

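### Table 7's Grade 2 liver rows for binimetinib are inconsistent: the liver-metastasis restart level is met at onset, some AST/ALT values fit rows with opposite actions, and restart ignores bilirubin

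*Combined protocol and SAP*

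**What the plan says.** Table 7 (Section 7.2.1.3, liver-related adverse events) sorts AST/ALT values into rows, most of them split by bilirubin at 2.0 x ULN.

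- **Grade 1**, above ULN up to 3 x ULN, at any bilirubin: "Maintain dose level of binimetinib".
- **Grade 2**, two rows, triggered by AST or ALT above "3 - 5.0 x ULN or 3 x baseline value) AND blood bilirubin" on one side or the other of 2.0 x ULN. Both say "Interrupt dose of binimetinib until resolved to Grade" 1 or lower, with an alternative of Grade 2 or lower for liver metastases ("2 in case of liver metastasis), then"). With bilirubin up to 2.0 x ULN, the dose is kept if resolution takes at most 14 days and reduced if it takes longer; a recurrence rule repeats the same restart level. With bilirubin above 2.0 x ULN, if the event resolves within 7 "days, resume treatment at a reduced dose of binimetinib"; otherwise binimetinib stops permanently.
- **Grade 3**, above 5.0 up to 8.0 x ULN with bilirubin up to 2.0 x ULN: the same instructions as the first Grade 2 row.
- **Permanent discontinuation**: above 8 x ULN with bilirubin up to 2.0 x ULN, or above 5.0 x ULN with bilirubin above 2.0 x ULN.

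The text above Table 7 bases decisions on the CTCAE grade and on the guidelines that follow it. It adds that Grade 1 toxicity should in general not lead to reduction or interruption. Table 4 (Section 6.1) admits AST/ALT up to 2.5 x ULN, or up to 5.0 x "ULN for participants with liver metastases".

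**The concern.** A dose-modification table works only if each laboratory result leads to one instruction. Here a site can follow the text faithfully and still hold binimetinib where another site continues it, or restart it where another stops it for good. In one row a participant can be restarted while the bilirubin that helped trigger the interruption is still raised. Liver test abnormality is a named overlapping toxicity for the three binimetinib combinations (Section 3.3.1, Table 1), so these rows are likely to be used. The first stake is participant safety. The second is uniform handling across sites, which matters when a dose is chosen from small groups.

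**Working it through.** **1. Restart level against trigger.** This step needs no arithmetic. A participant with liver metastases has a Grade 2 AST/ALT. The row says to interrupt until Grade 2 or lower. Grade 2 satisfies that on the day the event is recorded, so the interruption has no length. The fault is in both Grade 2 rows and in the recurrence rule of the row with bilirubin up to 2.0 x ULN. The Grade 3 row is sound on this point, because its restart level lies below its trigger.

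**2. The 3 x baseline arm.** Let b be baseline AST/ALT in multiples of ULN. I take the value at exactly 3b, the narrowest reading; reading the arm as at least 3b only widens the overlap. Setting 3b against the row limits:

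- 3b > 1 when b > 0.33, and 3b ≤ 3 when b ≤ 1: the Grade 1 row also applies.
- 3b > 5 when b > 5/3 = 1.67.
- 3b > 8 when b > 8/3 = 2.67.
- At the Table 4 maximum, 3 x 5 = 15 x ULN.

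| b | 3b | bilirubin ≤2.0 x ULN | bilirubin >2.0 x ULN |
|---|---|---|---|
| 0.3 | 0.9 | interrupt, at a value not above ULN | interrupt, at a value not above ULN |
| 0.5 | 1.5 | maintain and interrupt | maintain and interrupt |
| 1.2 | 3.6 | interrupt only | interrupt only |
| 2.0 | 6.0 | Grade 2 and Grade 3 rows, same action | interrupt and permanently discontinue |
| 3.0 | 9.0 | interrupt and permanently discontinue | interrupt and permanently discontinue |

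The baseline arm agrees with the Grade 2 row's own ULN range only for b above 1 and up to 1.67. For b from 1.67 to 2.67 with bilirubin up to 2.0 x ULN, two rows apply but their actions match. Table 4 admits b above 2.67 only with liver metastases. It admits b from 1.67 to 2.5 in any participant.

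**3. Bilirubin at restart.** Take AST 4 x ULN with bilirubin above 2.0 x ULN, both persisting. Without liver metastases, the participant is permanently discontinued after 7 days. With liver metastases, the stated AST/ALT level is met at once, and nothing in the row requires bilirubin to fall. The row's instruction is then to resume at a reduced dose. Section 7.2.1.3 allows no dose below 30 mg BID and requires discontinuation if a further reduction is needed, so this fault matters for participants taking 45 mg BID.

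**4. Could it reach the DLT count?** DLT item 9 is "Missing >25% of binimetinib doses as a result of drug-related AE(s) during the DLT period". Over 21 days BID there are 42 doses; 25% is 10.5, so 11 missed doses (5.5 days) qualify. Over 28 days there are 56 doses; 25% is 14, so 15 missed doses (7.5 days) qualify. In Cohort A the schedule has one chemistry panel per 21-day cycle. The next panel is Day 22, or Day 19 at the earliest with the 3-day window. Days 19 to 21 hold 3 x 2 = 6 doses, fewer than 11, so an unscheduled test would be needed.

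For the decision rule, Section 5.1.1.1 gives 4 DLTs in 6 as unacceptably toxic. With a Beta(1,1) prior (stated for the credible intervals, assumed here for the mTPI), P(rate > 0.30) is 0.971 at 4/6 and 0.874 at 3/6. An assumed cut of 0.95 therefore reproduces that example. With an assumed equivalence half-width of 0.03 or 0.05, one extra DLT moves 0/3 (escalate) to 1/3 (stay). Table 2 is redacted, so this step is conditional.

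**The case against.** The best reply is that the section already supplies a default: decide by CTCAE grade, and in general do not interrupt for Grade 1. On that view a rise from 0.5 to 1.5 x ULN is Grade 1 and treatment continues. This helps, but only in part. The rule is qualified, it defers in the same breath to the guidelines below it, and those label the same value Grade 2. If the ULN bands are meant to prevail, the baseline arm adds almost nothing and should say so. The default also does nothing for the liver-metastasis restart level.

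Table 7 gives recommendations, Section 7.2.1.1 provides for sponsor consultation in exceptional circumstances, and Section 5.1.2 requires sponsor discussion before dose adjustments in the DLT window. These soften the problem without saying which row applies. It is also natural to read the combined AST/ALT and bilirubin event as having to resolve as a whole. That may be the intent, but the row does not state it.

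A reader might infer more than the documents support:

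- *That a participant entering at 3 to 5 x ULN is already in breach of Table 7, or of Table 6.* Table 7 covers toxicity induced by binimetinib, and Table 6 covers immune-related events after other causes are considered. A permitted entry value is neither.
- *That one value can mean continue, interrupt and stop together.* This needs liver metastases, a baseline above 2.67 x ULN, and a value such as 9 x ULN treated as Grade 2 or lower. That is strained, since Table 7 already labels values above 5 x ULN with bilirubin up to 2.0 x ULN as Grade 3. Conflicts are normally between two actions.
- *That Section 9.3.7 is contradicted.* Its criterion ("an elevated AST or ALT lab value that is greater than or equal to 3X the upper limit of normal", with bilirubin and alkaline phosphatase conditions) is for reporting and does not govern dosing.

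**Conclusion.** The point holds, confined to the liver rows of Table 7 in Cohorts A, C and E. With liver metastases, every Grade 2 interruption is empty as written. At exactly 3 x baseline, the value conflicts with the maintain row for baselines above 0.33 and up to 1 x ULN. It conflicts with permanent discontinuation for baselines above 2.67 x ULN when bilirubin is up to 2.0 x ULN, and above 1.67 x ULN when bilirubin is higher. The restart test omits bilirubin in the one row where raised bilirubin is part of the trigger and restart is possible.

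This is mainly a participant-safety and consistency fault. A reader might infer that it biases the primary endpoint, but the documents support only a possible, indirect effect through DLT items 8 and 9. Cohort A would need an unscheduled test, and dose adjustments in the window go through the sponsor. Some values above 5 x ULN may already be DLTs under item 5, and item 8 does not say whether stopping binimetinib alone counts. An interruption that ends as it begins misses no doses. The documents do not give the distribution of baseline AST/ALT, so the number of participants affected cannot be stated.

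**What to change.** The sponsor must reconcile the Table 7 liver rows with each other and with the CTCAE-grade rule above the table, so that:

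- every combination of AST/ALT, baseline and bilirubin maps to one row, with the baselines to which the 3 x baseline arm applies stated, or a precedence rule given;
- the liver-metastasis restart condition differs from the Grade 2 trigger, including in the recurrence rule;
- the restart test covers bilirubin wherever bilirubin was part of the trigger.

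Which thresholds to use is for the sponsor's clinicians. The cost is an amendment to one table block and a notice to sites, with no added tests or participants.

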3.2.1.2.2 Binimatinib Clinical Studies

As of 20-JAN-2017, a total of 2750 healthy participants and patients have received at least 1 dose of binimatinib and are therefore eligible for inclusion in the overall safety population of binimatinib, which comprises 229 healthy participants, 164 patients with rheumatoid arthritis, 17 patients with hepatic dysfunction, 6 participants with renal dysfunction and 2334 patients with advanced cancer. Binimatinib demonstrated benefit over SOC agents in advanced melanoma as monotherapy as well as in combination with BRAF inhibitor [Ascierto, P. A., et al 2016] [Dummer, R., et al 2016] [Dummer, R., et al 2017]. The binimatinib clinical development program also includes ongoing trials in patients with mCRC including a Phase I trial investigating binimatinib in combination with mFOLFOX7 and a Phase I trial investigating binimatinib in combination with FOLFIRI.

In a Phase I dose-escalation study of oral binimatinib in patients with advanced solid tumors, common AEs (all grades) included combined rash, nausea, vomiting, diarrhea, peripheral edema, and fatigue. Ocular events were reported in 19% of patients. Most patients experienced Grade 2 (41%) or Grade 3 (49%) events. The most common Grade 3 events included anemia (11%), and abdominal pain and dehydration (4% each). Grade 4 AEs were reported for 6% of patients; those that occurred in at least 2 patients included anemia (3%).

There were no Grade 5 events. Laboratory abnormalities included increases in CPK and liver function tests [Bendell, J. C., et al 2017]. Of note, rash, ocular events, gastrointestinal events, increased CK, and edema are known class effects of MEK inhibitors [Larkin, J., et al 2014] [Bennouna, J., et al 2011] [Infante, J. R., et al 2012].

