- Hypertension CTCAE Grade ≥3 requiring more than 1 drug or more intensive therapy
- Grade 4 hypertension

13. Eye disorders

 Retinal

- Retinopathy or retinal detachment Grade ≥3, confirmed by ophthalmic examination
- Retinal vein disorder including RVO, confirmed by ophthalmic examination

 Visual disturbances without ocular (retinal) changes

- Blurred vision, flashing lights, floaters: Grade ≥3

 Other specify

- Grade ≥3 for >21 consecutive days
- Grade 4 confirmed by ophthalmic examination

If a participant experiences a DLT, trial treatment may be discontinued following discussion between the sponsor and Investigator. However, if the participant is deriving clinical benefit as determined by the Investigator from the trial treatment, the participant may be allowed to continue after discussion between the sponsor and the Investigator.

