7.2.1.3 Binimetinib

The starting dose level for binimetinib is 30 mg BID, and a dose reduction below 30 mg BID is not allowed. Participants requiring additional reductions must discontinue binimetinib treatment. Dose interruptions of more than 21 days are not allowed. In the cases of the dose interruption of longer than 21 days due to an AE, discontinuation of binimetinib should be considered.

For participants who do not tolerate the 45 mg BID dosing schedule, dose adjustment to 30 mg BID is permitted in order to allow the participant to continue on study drug.

Missed/skipped doses will not be made up (ie, the participant should not double their dose if the previous dose was missed). When the toxicity that resulted in a dose reduction improves to and remains stable at Grade 1 or less for a minimum of 21 days, the dose can be re-escalated at the investigators discretion provided there are no other concomitant toxicities.

No dose re-escalation of binimetinib is allowed after dose reduction due to left ventricular dysfunction or prolonged QTcF ≥ 501 msec.

No dose re-escalation of binimetinib is allowed after a dose reduction due to retinal toxicity \geq Grade 2.

Dose reduction/interruption/discontinuation decisions should be based on the CTCAE grade of the toxicity and the guidelines provided below. In general, doses should not be reduced or interrupted for Grade 1 toxicities, but treatment to control symptoms should be provided as appropriate.

Please refer to [Table 7](#) for dose adjustment recommendations for binimetinib-induced toxicities.

Table 7 Dose Modification Guideline for Binimatinib

Toxicity	Dose Adjustment for Binimatinib
Eye disorders- Retinal Events (including serous detachment of the retina)	
Grade 1	Maintain dose level of binimatinib and repeat ophthalmic monitoring including visual acuity assessment and ocular coherence tomography (OCT) within 10 days.
Grade 2	Interrupt binimatinib dosing and refer the participant to ophthalmologist within 1 week and obtain OCT within 10 days: 
 • If resolved to baseline or Grade ≤ 1 within 10 days, resume treatment at current dose level and continue schedule of visual assessments established per protocol. • If not resolved to baseline or Grade ≤ 1 within 10 days, resume treatment at reduced dose level and continue the schedule of events of visual assessments established per protocol.

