Grade 3 ($> 5.0 - 10.0 \times$ ULN) without renal impairment (ie, serum creatinine $< 1.5 \times$ ULN or 1.5 x baseline)	
If asymptomatic, maintain dose of binimetinib. Monitor closely and measure isoenzymes and myoglobin in blood and urine.
 
If symptomatic (muscle pain/spasms or muscle weakness), interrupt dose of binimetinib until resolved to CTCAE Grade \leq 1 and monitor closely, then:
 
 • If resolved in \leq 21 days, reduce 1 dose level of binimetinib. • If resolved in $>$ 21 days, permanently discontinue binimetinib.
Grade 4 without renal impairment (ie, serum creatinine $< 1.5 \times$ ULN or 1.5 x baseline)	
If asymptomatic, interrupt dose of binimetinib and monitor closely. Ensure patient is adequately hydrated and monitor and measure isoenzymes and myoglobin in blood or urine, and serum creatinine.
 
 • If resolved in \leq 21 days, reduce 1 dose level of binimetinib. • If resolved in $>$ 21 days, permanently discontinue binimetinib. 
If symptomatic, permanently discontinue binimetinib.
 
If symptomatic (muscle pain/spasms), permanently discontinue binimetinib.

Grade 3 or 4 with renal impairment (ie, serum creatinine $\geq 1.5 \times$ ULN or 1.5 x baseline)	
Interrupt binimetinib dose until resolved to Grade $<$ 1 or baseline level. Ensure patient is adequately hydrated. Monitor isoenzymes and myoglobin in blood or urine, and serum creatinine, then:
 
 • If resolved in \leq 21 days, reduce 1 dose level of binimetinib. • If resolved in $>$ 21 days, permanently discontinue binimetinib. 
Recurrence:
 
 • Permanently discontinue binimetinib

Toxicity	Dose Adjustment for Binimetinib
Rash	
Grade 1	Treatment with binimetinib should be maintained at the current dose. Initiate prophylactic regimen if it was not already and monitor closely.

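### Table 7 lets symptomatic Grade 4 CK elevation with renal impairment restart binimetinib, while the same event without renal impairment is a permanent stop

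*Combined protocol and SAP*

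**What the plan says.** The CK block of Table 7 (Section 7.2.1.3) splits Grade 3 and Grade 4 elevations by renal function.

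- **Grade 4 without renal impairment.** Asymptomatic participants interrupt binimetinib. They resume one level lower if the event resolves within 21 days and otherwise stop permanently. For symptomatic participants the cell says "If symptomatic (muscle pain/spasms), permanently discontinue binimetinib", and it gives that instruction twice.
- **"Grade 3 or 4 with renal impairment".** One row covers both grades, with no division by symptoms. Binimetinib is interrupted until CK falls below Grade 1 or returns to baseline. If that takes 21 days or less, the instruction is to "reduce 1 dose level of binimetinib". Slower recovery, or a recurrence, is a permanent stop.

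The text of Section 7.2.1.3 sets the floor: "a dose reduction below 30 mg BID is not allowed". A participant who would need a further reduction must come off binimetinib.

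**The concern.** A dose-modification table should not become more permissive as the presentation worsens. Muscle symptoms with Grade 4 CK and a raised creatinine is a worse picture than the same event with normal creatinine, yet only the former has a route back to binimetinib.

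The rest of Table 7 suggests this was not intended. In the liver rows, a second signal (bilirubin above 2 x ULN) tightens the rule: AST or ALT above 5 x ULN becomes a permanent stop, and Grade 2 must resolve within 7 days or binimetinib ends. Grade 4 is a permanent stop for retinal and other eye events, AST/ALT, rash, nausea or vomiting, pneumonitis and the catch-all row. Grade 4 diarrhea is an exception. No reason is given for easing the CK rule when creatinine rises.

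What is at stake is participant safety: re-exposure after a severe muscle event with kidney involvement. The event is foreseeable in kind, since Section 3.2.1.2.2 states that "increased CK, and edema are known class effects of MEK inhibitors".

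**Working it through.** The plan states no figure to reproduce. The check compares the CK rows and then counts whom the row can reach.

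**Step 1. The four combinations, first occurrence.**

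| CK event | Without renal impairment | With renal impairment | Renal row is |
|---|---|---|---|
| Grade 3, asymptomatic | Maintain dose, monitor | Interrupt to below Grade 1 or baseline; restart one level lower if within 21 days | Stricter |
| Grade 3, symptomatic | Interrupt to Grade 1 or less; restart one level lower if within 21 days | As above, with a lower recovery threshold and a stop on recurrence | Stricter |
| Grade 4, asymptomatic | Interrupt; restart one level lower if within 21 days | The same, plus a stop on recurrence | Stricter |
| Grade 4, symptomatic | Permanent stop | Interrupt; restart one level lower if within 21 days | More lenient |

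One combination of four is out of order.

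**Step 2. Dose.** Binimetinib is given at 30 or 45 mg BID. At 30 mg BID no reduction is available, so the participant stops whichever row applies. Only someone on 45 mg BID at the time of the event can restart, at 30 mg BID.

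**Step 3. Participants governed.** Binimetinib is given in Cohorts A, C and E. Section 10.9 caps each Part 1 dose level at 14 and adds about 16 in Part 2 at the RP2D. Participants treated at 45 mg BID per cohort are therefore:

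- 0 if the dose is never opened;
- up to 14 if it is tried but not chosen;
- about 14 + 16 = 30 if it is the RP2D.

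Over three cohorts the range is 0 to 3 x 30 = 90. The top end needs 45 mg BID to be the RP2D in all three.

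**Step 4. How often.** The documents give no rate for symptomatic Grade 4 CK with renal impairment. The nearest figure is in Section 3.2.1.2.2: two treatment-related CPK elevations of Grade 3 or higher in the study of binimetinib with mFOLFOX7, before any condition on symptoms or creatinine. That is not a rate for this trigger, so no expected count is calculated.

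**The case against.** The strongest reply is that other clauses already govern such a case.

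- Section 8.1 requires study treatment to stop for unacceptable adverse events and lets the investigator stop for any untoward effect.
- The catch-all row of Table 7 permanently stops study drug for other related Grade 4 events. Appendix 5 asks for the diagnosis to be recorded rather than its signs, so a separate diagnosis graded 4 would trigger that row.
- Section 7.2.1.1 sends exceptional departures from the tables to the Sponsor.
- Section 5.1.3 says "If a participant experiences a DLT, trial treatment may be discontinued following discussion between the sponsor and Investigator".
- Appendix 5 requires advance Sponsor approval for rechallenge after a serious event that the product may have caused.

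These safeguards are real, and the Sponsor could refuse a rechallenge. They narrow the gap without closing it. The catch-all row helps only if a separate diagnosis reaches Grade 4. The DLT discussion covers 21 or 28 days of treatment that may last two years, and it may end in continuation. The rest depend on judgement or approval, and the approval clause refers back to the dose-modification guidelines.

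The doubled sentence in the Grade 4 cell also hints at a drafting or layout slip; the second copy may have been meant for the renal row. As the table reads, it comes before that row's label, so the renal row has no symptom condition.

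Two stronger readings are tempting. First, a reader might infer that the cardiac rows show a second inversion, because an unrecovered asymptomatic LVEF fall ends study treatment while Grade 3-4 dysfunction ends only binimetinib. The documents do not support that: the column is headed as binimetinib dosing and the row opens by interrupting binimetinib. This is loose wording. Second, a reader might count re-escalation as part of the CK problem. Section 7.2.1.3 allows it once the toxicity "remains stable at Grade 1 or less for a minimum of 21 days, the dose can be re-escalated at the investigators discretion", and CK is not among the listed bars (such as "No dose re-escalation of binimetinib is allowed after dose reduction due to left ventricular dysfunction or prolonged QTcF"). But that applies after any CK-related reduction, with or without renal impairment, so it is not part of the inversion.

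**Conclusion.** The concern holds for one row. For symptomatic Grade 4 CK elevation, Table 7 gives the presentation with renal impairment the more lenient action. The reach is narrow: a first occurrence, on 45 mg BID, in Cohort A, C or E, with recovery below Grade 1 or to baseline within 21 days. The row governs 0 to about 90 participants; the number who would meet the trigger is unknown and likely small.

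A reader might go further and infer that the plan compels re-exposure or that the trial's results are affected. Neither follows. Investigators and the Sponsor can stop treatment, and no endpoint, DLT definition or sample size changes. What remains is a written default that points the wrong way for the worst CK presentation, which should be corrected. The conclusion assumes that the table's cell boundaries are as they read in the protocol.

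**What to change.** In the row for Grade 3 or 4 CK elevation with renal impairment, add: *If Grade 4 and symptomatic, permanently discontinue binimetinib.* This brings it into line with the Grade 4 row without renal impairment. The duplicate sentence in that Grade 4 cell can be deleted at the same time.

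The change needs no added participants, visits or procedures. Its clinical cost is that a few participants on 45 mg BID lose the option of restarting at 30 mg BID.
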